## STATISTICAL DESIGN AND POWER

Descriptive statistics and exploratory graphing will be generated for all variables of interest measured at all time points (i.e., baseline, mid-treatment, post-treatment, 3-month follow-ups). Data summaries will be produced both for the combined sample, and separately by treatment condition. Variables will be transformed if necessary using Box-cox power transformation. Baseline characteristics will be compared between treatment conditions using ANOVA (or non-parametric Kruskal Wallis test, as appropriate) for continuous variables and a chi-square test for categorical variables. Key baseline variables that differ by condition will be considered for use as covariates in the analyses described below.

**Primary Aim 1.** To assess feasibility and acceptability, we will use the following benchmarks: (a) recruitment success: enrollment of 60 patients; (b) attrition: retention of >75% of patients through all assessments; (c) study retention: patients attend at least 90% of all treatment groups; (d) satisfaction: patients express high satisfaction with RRT based on feedback questionnaires.

**Primary Aim 2.** To evaluate the effect of each treatment condition on hypothesized targets, we will model the pattern of change in reward response to palatable food, reward response to day-to-day life activities, social isolation, and loneliness separately over time using multilevel models (PROC MIXED in SAS). The first level will model individual participant's score on the relevant target over time with baseline as time 0. At the second level, the individual intercept and slope will be entered as outcomes with treatment condition as a predictor. We will examine each treatment condition separately. The cross-level interaction between time and treatment condition will be used to determine the effect of treatment condition on the pattern of change in the hypothesized targets. Restricted maximum likelihood will be used to estimate model parameters and to test the significance of random effects. Both linear and higher-order time effects will be examined based on model selection criterion such as Akaike Information Criterion (AIC) and Bayesian Information Criterion (BIC). With the fitted multilevel model structure, statistical contrasts will be performed at mid-treatment, post-treatment, and 3-month follow-up.

We will conduct mediation analysis to determine whether temporally-precedent changes in the hypothesized targets mediate differences in the primary outcomes between the two treatment conditions. In particular, we will examine improvement in each hypothesized target from baseline to mid-treatment assessment predicting post-treatment outcomes and improvement at post-treatment predicting 3-month follow-up outcomes. We will use the mediation model outlined by Preacher and Hayes to estimate the total and specific indirect effects of each hypothesized mediator individually. The bias-corrected bootstrap test will be applied to test the joint significance of the indirect pathways. This approach expands on Baron and Kenny's methods by providing additional guidelines and techniques that allow for the most robust and accurate interpretation of these mediating effects. Should these mediation analyses prove promising, we will explore how the entire pattern of changes in the mediators from baseline to later time periods (mid-treatment and post-treatment assessments) influences the corresponding pattern of outcomes over time using the parallel process growth models.

**Primary Aim 3.** Analyses will be conducted via linear mixed effects models for longitudinal data, which increase power by fully exploiting the strong correlation in treatment outcomes of interests (i.e., percent binge frequency reduction and percent change in EDE global eating pathology) across time. Patterned covariance matrices as implemented in (PROC MIXED in SAS) and will be used to evaluate between group differences for percent binge reduction and percent change in EDE global eating pathology across the study as a whole, and at each assessment post-baseline. Separate variance components will be used to capture therapist and participant-within-therapist variation. The within-subject covariance matrix will be assumed common across study arms, with an exponential variance function to deal with heteroscedasticity and a continuous-time AR(1) correlation matrix to accommodate residual autocorrelation over the unequal-size time intervals between follow-ups. Outcomes at all four time points will be estimated jointly for maximum statistical efficiency in the presence of intermittent missingness and loss to follow-up. The model will include random effects for subject and time (with higher-order effects if needed to capture nonlinear change), and fixed effects for treatment arm, time by treatment interaction, demographic information, and baseline values of binge frequency and global eating pathology. Time-specific covariate-adjusted contrasts will be used to compare outcome between groups.

**Secondary Aim 1.** We will use the same analytic approach described above for Primary Aim 3 but will test the impact of treatment condition on secondary outcomes including depression, substance abuse, and quality of

life.

**Attrition.** Patterns of missing data will be examined. Likelihood-based estimation methods and multiple imputation models will be used to handle missing data. In addition, we will use Hedeker and Gibbons' procedure to examine if dropouts influence the multilevel model results. If the missingness mechanism is related to the missing outcome itself, we will use sensitivity analyses to explore how robust our findings are with respect to a range of assumptions regarding missing data.

**Power analyses.** Using the method described by Raudenbush and implemented with the software Optimal Design, power calculations were made for mixed effects models. A sample size of 154 (77 for each condition) is required for 80% power to detect a medium effect with the significant level of 0.05 and four assessment points, assuming the ratio of the variability of level-1 coefficient to the variability of level-1 residual is one. Fritz and MacKinnon documented sample size requirements to guarantee 80% power at the significance level of 0.05 for mediation models. Under the assumption of a medium effect for intervention with the mediator and a medium effect for the mediator on outcome controlled for intervention, the required sample size is 72 in total with 36 per intervention arm to achieve 80% power in simple mediation models. Given our relatively small sample size ( $n=60$ ), our study is powered to detect large effect sizes. While we observed large effect sizes in our pilot trial of RRT compared to a wait list control, we anticipate that the effect sizes may be smaller in the current trial as supportive therapy is an active treatment condition. It is likely that we may be underpowered for formal tests of statistical significance in this preliminary study. We will rely on effect sizes for interpretation when underpowered.

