## **A.7. Current study and specific aims.**

In the current study, we will revise our existing 10-session group RRT treatment manual to specifically address the challenges in building social support and enhancing both momentary and sustained reward during the COVID-19 pandemic (Preliminary Aim 1). In months 2-18, we will conduct a small pilot RCT that will randomize individuals to receive either 10-sessions of RRT (n=30) or supportive therapy (n=30), both delivered as group-treatments via videoconferencing software. The specific aims of the current study are to confirm the feasibility and acceptability of RRT for EDs (Primary Aim 1), evaluate the ability of RRT to engage critical targets including reward to day-to-day life activities, reward to palatable foods, social isolation, and loneliness (Primary Aim 2), and provide preliminary estimates of efficacy in reducing ED symptoms at both post-treatment and a 3-month follow-up (Primary Aim 3). We will also evaluate the impact of RRT on secondary outcome variables including depression, substance use, and quality of life (Secondary Aim 1).

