## D. Approach

**D.1. Participants.** 60 participants will be recruited for this study. Participants must: A.) be age 18-65, and B.) have a diagnosis of either BN or BED. Individuals will be excluded if they are 1) below a BMI of 17.5, 2) are already receiving treatment for an ED, 3) require immediate treatment for medical complications as a result of eating disorder symptoms, or 4) are experiencing other severe psychopathology that would limit the participants' ability to comply with the demands of the current study (e.g. severe depression with suicidal intent, active psychotic disorder). Participants will be screened by phone to assess preliminary eligibility. Phone screens will use questions from the Mini International Neuropsychiatric Interview (MINI) to assess psychiatric comorbidity and will be conducted by trained doctoral students, similar to procedures used successfully in our teams other NIH trials.

**D.2. Refining RRT for use during the COVID-19 pandemic.** In month 1, we will revise our existing RRT manual to facilitate delivery via videoconferencing software by applying "lessons learned" from our ongoing remote groups for R01DK117072. For example, we will add instructions to use video conferencing features such as breakout rooms to facilitate in-session experiential activities and whiteboards to facilitate 'real-time' collaborative problem-solving. We will also revise the content of the RRT manuals to provide guidance on ways to build and maintain social connections during the COVID-19 pandemic as in-person social contact is limited (e.g., connecting with neighbors on Facebook group, scheduling virtual game nights with friends, enhancing intimacy with romantic partners during at home dates, attending virtual happy hours with colleagues), and address disruptions in current relationships due to the pandemic (e.g., conflict due to the switch to telework/teleschool). Participants will be encouraged (though not required) to connect with each other outside of group using email, texting, and social networking platforms to enhance social support outside of weekly sessions.

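### Extra covariates are chosen by testing for baseline differences between randomised arms, while diagnosis (BN or BED) is pre-specified in no model: a loss of precision, not an inflated error rate

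*SAP*

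**What the plan says.** The SAP's opening paragraph (STATISTICAL DESIGN AND POWER) plans between-arm tests at baseline: "Baseline characteristics will be compared between treatment conditions using ANOVA (or non-parametric Kruskal Wallis test, as appropriate) for continuous variables", and chi-square for categorical ones. It continues: "Key baseline variables that differ by condition will be considered for use as covariates in the analyses described below". It gives no list of key variables, no threshold for a difference, and no rule for what follows from considering one. The sentence covers every analysis after it.

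The models themselves name these covariates:

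- **Primary Aim 2** (targets): at level 2, "the individual intercept and slope will be entered as outcomes with treatment condition as a predictor". Baseline is time 0 of the response. No other covariate is named.
- **Primary Aim 3** (percent binge reduction, percent change in EDE global): besides arm and time by arm, the fixed effects are "demographic information, and baseline values of binge frequency and global eating pathology". The demographics are not itemised.
- **Secondary Aim 1** (depression, substance use, quality of life): "We will use the same analytic approach described above for Primary Aim 3". The baselines of these outcomes are not named.

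Protocol D.1 admits participants who "have a diagnosis of either BN or BED". No model lists diagnosis, and neither document mentions stratifying the randomisation by it.

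**The concern.** When allocation is random, any baseline difference between arms is chance. A covariate improves a randomised comparison because it predicts the outcome, not because it happens to be unbalanced. A rule that acts on imbalance leaves out prognostic variables that look balanced, may bring in irrelevant ones that do not, and leaves the model open until data by arm have been seen.

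Diagnosis is the clearest case. The sample mixes two disorders, the variable is known for everyone at entry, and it can reach a model only by differing between arms. The stake is the precision of the effect estimates. That matters here because the SAP's power section says interpretation will rest on effect sizes where the trial is underpowered.

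**Working it through.** **Inputs.** From the documents: 60 participants, 30 per arm (Protocol A.7); significance level 0.05, four assessments, variance ratio 1, required N of 154 (SAP, Power analyses). Assumed, because the documents do not say: medium effect = 0.5 SD, large = 0.8 SD, two-sided tests, a difference at baseline means p<0.05, BN:BED mix 50:50 or 30:70, and the correlation r of diagnosis with outcome.

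**1. The plan's own figure.** The SAP states: "A sample size of 154 (77 for each condition) is required for 80% power to detect a medium effect". Power for a difference in linear slopes uses a noncentral F(1, N−2) with λ = N·δ²·ρ/4 and ρ = τ/(τ+V). With four equally spaced points the squared time deviations sum to 5, so V = 1/5 = 0.2 and ρ = 1/1.2 = 0.833. At N = 154, λ = 154 × 0.25 × 0.833/4 = 8.02 and power is 80.4%. The figure reproduces. At N = 60 the same formula gives 41% for an effect of 0.5 and 79% for 0.8, so there is little precision to spare.

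**2. How often the rule fires.** One variable is flagged in 5% of trials. At least one of K independent variables is flagged with probability 1 − 0.95^K: 23% for K = 5 and 40% for K = 10. A prognostic diagnosis would be adjusted for in about 1 trial in 20.

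**3. Whether it catches imbalance.** By exact binomial calculation with 30 per arm, a BN/BED imbalance of 20 points or more occurs in 15.5% of trials at 50:50 and 12.0% at 30:70. In 66% and 60% of those trials, respectively, the uncorrected chi-square test has p ≥ 0.05. Example: 12/30 against 18/30 gives p = 0.12. At 50:50 the BN–BED outcome difference is 2r SD, so a 20-point imbalance moves the unadjusted effect by 0.20 × 2r: 0.04, 0.12 or 0.20 SD at r = 0.1, 0.3 or 0.5.

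**4. Power and type I error.** Simulation with 30 per arm, one endpoint, a 50:50 mix, diagnosis the only covariate, and 20,000 runs per scenario:

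| r | Power at 0.5: fixed / rule | Power at 0.8: fixed / rule | Type I error: fixed / rule |
|---|---|---|---|
| 0.1 | 47.4% / 47.3% | 85.9% / 86.2% | 4.8% / 4.8% |
| 0.3 | 50.7% / 47.5% | 88.4% / 86.5% | 5.1% / 4.8% |
| 0.5 | 58.7% / 47.8% | 93.3% / 86.8% | 5.0% / 4.2% |

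The loss is about 0, 2 to 3, and 6 to 11 points. A 30:70 mix gives much the same. With 5 or 10 tested covariates, type I error under the rule was 3.8% to 4.9%. The variance of the estimate under the rule, relative to fixed adjustment, is no higher at r = 0.1, about 6% higher at 0.3 and about 22 to 23% higher at 0.5.

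**5. With the baseline outcome already in the model** (correlation 0.5 with outcome), five tested covariates and an effect of 0.5 (8,000 runs), fixing all five against the rule gives 59.7% against 57.3% if they explain 10% of variance, and 77.1% against 60.1% if they explain 30%. A long list of weak covariates does not help: ten that explain 10%, with no baseline outcome in the model, give 43.9% fixed against 44.8% under the rule.

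**6. Aim 2.** The test there is time by treatment. Simulation used n = 60, four visits, random intercept and slope, and balanced complete data. A diagnosis main effect left the SD of that estimate unchanged (0.288 with or without it). When diagnosis was assumed to affect slopes, the SD was 0.328 with or without the main effect and 0.292 with diagnosis-by-time. A separate run gave 0.315 and 0.296. The size of this gain depends on the assumed slope effect.

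**Limits.** Steps 4 and 5 use a single time point, with no therapist or group clustering and no dropout. Monte Carlo error is about 0.2 points on type I error and 0.4 to 0.6 on power.

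**The case against.** The strongest reply is that Aim 3 does not depend on the rule. It fixes demographics and the two baseline severity measures in advance, and the opening sentence only adds variables to be considered. For the primary outcomes, what matters is how much diagnosis adds once baseline severity is in the model, and the documents give no figure for that. The loss is nil at a correlation of 0.1. This is also a 60-person pilot that concedes low power, so a few points may not change the decision it informs. All of this stands, and it sets the size of the point. It does not justify the rule: estimates are what the pilot will produce, and the rule leaves most sizeable diagnosis imbalances unadjusted.

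A reader might infer more than the documents support:

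- *That all covariates are picked by testing.* Aim 3 shows otherwise.
- *That diagnosis is barred.* It can enter if it differs by arm.
- *That the rule produces extra false positives.* Applied as a fixed p<0.05 rule it is slightly conservative. Inflation would need a choice driven by outcome results. The loose wording leaves room for that, but the SAP does not plan it.
- *That diagnosis is needed because remission counts compensatory behaviours (Protocol D.6.2).* The SAP has no remission model.
- *That Aim 2 ignores baseline.* Baseline is its time-0 response.

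On Secondary Aim 1, the authors may intend each outcome's own baseline to replace the two named ones. The text does not say so.

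**Conclusion.** The concern holds in limited form. The SAP selects additional covariates on chance imbalance, without a list or threshold, and pre-specifies diagnosis nowhere. The consequence falls mainly on diagnosis in every model, on Aim 2, and on Secondary Aim 1. Validity is not threatened: type I error stays at about 4 to 5%. The cost is precision, from nothing to 6 to 11 points of power across assumed correlations of 0.1 to 0.5, for diagnosis with no other covariate in the model. That range should not be carried over unchanged to Aim 3, where baseline severity is already adjusted for. The change is worth making because it uses data already in hand and costs almost nothing.

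**What to change.** - Delete the sentence that selects covariates by baseline difference. Present the baseline table descriptively, without tests.
- **Aim 3:** add diagnosis (BN or BED) to the fixed covariates, and itemise the demographics so that the list is closed before data by arm are seen. Keep it short (step 5).
- **Secondary Aim 1:** add diagnosis and name the baseline value of each secondary outcome as a covariate in its own model.
- **Aim 2:** add diagnosis and diagnosis-by-time at level 2. Do not add the baseline outcome as a covariate, because it would then stand on both sides of the model.

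Cost: SAP wording, plus one degree of freedom for diagnosis (two in Aim 2 with linear time). Diagnosis is already established for eligibility. If it proves weakly prognostic the loss is negligible: at r = 0.1, fixed adjustment and the rule differ by at most 0.3 points of power.

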## **A.6. Preliminary results of RRT suggest the promise of this intervention paradigm, but additional research is needed to determine whether a fully powered trial is worth pursuing.**

In a recent pilot study of RRT, we randomized 19 individuals with transdiagnostic binge eating to receive either RRT or a wait-list control. As described in greater detail in the *Preliminary Studies* section below, we found preliminary support for the feasibility, acceptability, target engagement, and clinical impact of RRT. However, despite the promise of our early pilot data, we believe that a more rigorous pilot RCT with an active control condition and with follow-up data would allow us to determine whether RRT is worth testing as a treatment approach for transdiagnostic binge eating in a fully powered clinical trial. We also believe that there is considerable benefit to leveraging our existing clinical research infrastructure (see *Recruitment and Retention* plan for additional details) to evaluate RRT during the COVID-19 pandemic given that RRT is particularly well-suited to address the disruption to social networks and resulting impact on day-to-day reward that has occurred due to COVID-19. The proposed study is consistent with the research priorities outlined in NOT-MH-20-047 (e.g. *Research to identify potential intervention targets for modifying social connectedness, isolation, and/or loneliness via social media and/or electronic communication to prevent the development of clinically significant mental health symptoms*.)

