**D.5. Remote study procedures.** Study assessments and group therapy sessions will be conducted using an encrypted HIPAA-compliant version of Zoom videoconferencing software which we are currently using in several NIH-funded clinical trials during the stay-at-home orders. Informed consent will be collected using an electronic consent form that participants will be asked to complete during the appointment after reviewing the consent form jointly with a staff member.

**D.6. Assessments.** Assessments will be conducted by blinded assessors at baseline, mid-treatment (after session 5), post-treatment (after session 10), and at a 3-month follow-up. Our assessment strategy was specifically designed to allow for remote assessment during the COVID-19 pandemic and thus will only include measures that can be completed using videoconferencing or via the participants home computer. In order to maximize assessment completion, we will increase compensation across assessments (\$50, \$75, \$100, \$125).

**D.6.1. Feasibility and Acceptability.** Assessment of feasibility will include % of eligible patients enrolled, attrition, and study retention. We will use a Feedback Questionnaire (FQ) to obtain qualitative acceptability ratings, which will be modified from FQs used in our prior intervention development projects.

**D.6.2. Primary outcomes.** The Eating Disorder Examination is a widely utilized, semi-structured interview for the assessment of eating disorder symptoms. We will use number of binge episodes in the last 28 days and EDE global scores as the primary outcomes. Remission status will also be evaluated at each assessment following the baseline assessment and will be defined as the absence of any binge episodes or compensatory behaviors in the 28 days prior to the assessment point and an EDE global score within 1 standard deviation of the community norm (EDE global <1.74).

**D.6.3. Secondary outcomes.** We chose to use commonly-used and well-validated measures of depression (Beck Depression Inventory-II), substance use (Alcohol, Smoking, and Substance Involvement Screening Test), and quality of life (Quality of Life Inventory) to assess secondary outcome measures.

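### Should the Primary Aim 1 retention and attendance benchmarks be tied to the RRT arm, given that the SAP names no arm for either?

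*SAP*

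**What the plan says.** Protocol A.7 gives the aim as to "confirm the feasibility and acceptability of RRT for EDs (Primary Aim 1") and plans 30 participants for RRT and 30 for supportive therapy. Protocol A.6 adds that a more rigorous pilot trial "would allow us to determine whether RRT is worth testing as a treatment approach for transdiagnostic binge eating in a fully powered clinical trial".

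The SAP, under Primary Aim 1, sets four benchmarks:

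- (a) enrolment of 60, which is necessarily the whole trial;
- (b) "retention of >75% of patients through all assessments";
- (c) "patients attend at least 90% of all treatment groups";
- (d) "patients express high satisfaction with RRT based on feedback questionnaires".

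Only (d) names RRT. Protocol D.6.1 names no arm either: "Assessment of feasibility will include % of eligible patients enrolled, attrition, and study retention". The opening paragraph of the SAP states: "Data summaries will be produced both for the combined sample, and separately by treatment condition". No section says which of those summaries a benchmark is judged on.

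**The concern.** The aim is about RRT, but (b) and (c) speak only of patients, soon after a benchmark that counts all 60. A reader could well take them as pooled. Half of a pooled sample receives supportive therapy, so good control retention could hide poor retention in RRT, and poor control retention could make RRT look infeasible when it is not. Because the pilot is meant to inform a decision about a full trial of RRT, a misread verdict could push that decision the wrong way. An open denominator also leaves room to choose between two verdicts after the data are seen. Benchmark (c) has a second gap: it does not say whether 90% is a mean or must be reached by each patient.

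**Working it through.** The 75% is a chosen cut-off, so there is no calculated figure to reproduce. The check is how often the two readings give different verdicts.

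**Inputs.** 30 per arm (Protocol A.7); retention above 75% and attendance of at least 90% (SAP, Primary Aim 1). Protocol C.1.1, from the team's group trial in binge eating disorder, gives drop-out of 5.0% (remote) and 14.0% (in person), so 95% and 86% retained, and attendance of 96.5% and 85.0%. Every other true rate below is an assumption.

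**Cut-offs as counts.** The inequality is strict, so the minimum is floor(0.75 × n) + 1.

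- Pooled: floor(45) + 1 = 46 of 60; 45/60 = 75.0% fails.
- RRT only: floor(22.5) + 1 = 23 of 30; 22/30 = 73.3% fails.

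**Disagreement is possible both ways.**

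- Pooled met, RRT short: 22 + 24 = 46; at the extreme, 16 + 30 = 46.
- Pooled missed, RRT meets it: 23 + 22 = 45; or 27 + 18 = 45.

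**How often.** Let X and Y be the numbers retained in RRT and control, independent binomials on 30 each. Disagreement is P(X + Y ≥ 46 and X < 23) + P(X + Y < 46 and X ≥ 23).

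| True retention, RRT / control | Pooled met, RRT short | Pooled missed, RRT met | Total |
|---|---|---|---|
| 95% / 95% | 0.0001 | 0.0000 | 0.0001 |
| 95% / 86% | 0.0001 | 0.0003 | 0.0004 |
| 86% / 95% | 0.049 | 0.000 | 0.049 |
| 86% / 86% | 0.040 | 0.007 | 0.047 |
| 75% / 75% (assumed) | 0.093 | 0.157 | 0.250 |
| 80% / 70% (assumed) | 0.024 | 0.335 | 0.359 |
| 70% / 90% (assumed) | 0.520 | 0.001 | 0.521 |

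In the first four rows, built from the documents' own rates, the readings differ at most about 5% of the time. Most of that arises with RRT truly at 86%, where the pooled rule passes and the RRT-only rule fails by chance. Since 86% exceeds 75%, the pooled verdict is then the right one.

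**Would an RRT-only rule do better?** Take a wrong verdict to be passing RRT when its true rate is below 75%, or failing it when above.

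| True retention, RRT / control | Error | RRT-only | Pooled |
|---|---|---|---|
| 70% / 70% | wrong pass | 28.1% | 16.2% |
| 80% / 80% | wrong fail | 23.9% | 20.7% |
| 86% / 86% | wrong fail | 5.0% | 1.6% |
| 70% / 86% | wrong pass | 28.1% | 66.8% |
| 86% / 70% | wrong fail | 5.0% | 33.2% |

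With equal arms the pooled rule errs less. It becomes the worse rule when control exceeds about 75% with RRT at 70%, or drops below about 82% with RRT at 86%: a gap of 4 to 5 points. Precision also favours pooling: the exact 95% interval is 58% to 90% for 23/30 and 64% to 87% for 46/60.

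**Attendance.** If (c) is a mean with equal arms, the RRT mean at which the pooled figure is exactly 90% is 2 × 90 − control. With control at 96.5% this is 180 − 96.5 = 83.5%; with control at 85.0% it is 180 − 85.0 = 95.0%. If both arms attend at the remote rate of 96.5%, both readings are met. If instead every patient must reach 90%, a pooled pass implies an RRT pass, and only the opposite disagreement is possible.

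**The case for a change.** The strongest case for a change is that the aim is worded as the feasibility of RRT and the text permits two verdicts from the same data. Summaries by condition carry no threshold, so they show the RRT figure without saying whether it passes. The two arms differ by design: supportive therapy is non-directive (Protocol D.3), while the RRT revisions encourage contact outside sessions (D.2). The reassuring rates come from a different trial, without bulimia nervosa, a supportive therapy arm or a 3-month follow-up, and its remote figures rest on one wave. A benchmark matters most when retention turns out worse than hoped. And the SAP concedes that significance tests may be underpowered, which gives the feasibility results more weight.

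Much of this stands. The denominator is unstated, the C.1.1 rates may be optimistic for completion of all assessments, and with retention near 75% or a wide gap between arms the readings would often part. What does not stand is the step from there to a flaw. Pooling is inferred; given A.7, an analyst could equally apply (b) and (c) to RRT. Different content does not establish different retention: both arms are videoconference groups run by clinicians from the same clinic (D.4), with the same assessment schedule and rising payments (D.6). The large disagreement figures rest on assumed rates that appear nowhere in the documents.

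**Conclusion.** No change to the plan is needed. This is missing detail that analysts can fill sensibly, and the one substantive alternative is a fair trade-off.

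- **The information will be there.** The SAP commits to summaries by condition. Retention and attendance are not named in that sentence, but reporting them by arm is ordinary practice in a two-arm trial. Retention of 16/30 in RRT would be plain to see, and no automatic decision rule or test would override it.
- **A pooled (b) has its own use.** Completing every assessment is a trial procedure common to both arms, and poor control retention bears on whether a full two-arm trial is workable. It does not by itself answer the question about RRT, for which the RRT figure is the evidence.
- **Restricting to RRT has a price.** It protects against a gap between arms, but errs more often when they retain equally: 28.1% against 16.2% wrong passes at 70%, and 5.0% against 1.6% wrong fails at 86%.

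The size is small on the documents' own related rates (disagreement of at most about 5%) and larger only under assumed rates near 75% or gaps of 10 to 20 points. This rests on 30 per arm, independent outcomes between participants, and retention resembling that in C.1.1. Stating the denominator, and whether (c) is a mean, would be a harmless clarification rather than a correction.
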